8.1 Study Drug

Dapagliflozin, an SGLT2 inhibitor, is available as 5mg and 10mg tablets. Each bottle containing 50 of the 10 mg tablets will be purchased using funding from American Heart Association.

8.2 Dosing

Subjects randomized to the dapagliflozin-then-placebo arm, will be instructed to administer dapagliflozin 10mg once daily for 6 weeks. Week 7 & 8 will be provided as a washout period. Afterwards, subjects will receive the placebo 0mg once daily for the remainder 6 weeks. The dose has been selected based on prior studies demonstrating the impact on cardiovascular health at the dose of 10mg and the safety profile is well-established with starting at the 10mg dose from multiple studies both including individuals with and without Type 2 diabetes with an acceptable safety profile.

Subjects randomized to the placebo-then-dapagliflozin arm, will be instructed to administer placebo 0mg once daily for 6 weeks. Week 7 & 8 will be provided as a washout period. Afterwards, subjects will receive the dapagliflozin 10mg once daily for the remainder 6 weeks.

8.3 Administration of Dapagliflozin

Subjects will receive Dapagliflozin 10mg capsules, to fulfill the 6 weeks treatment plus 3 tablets to account for lost doses. Subjects will be instructed to take 1 capsule (10mg) by mouth once daily preferably in the morning with or without food.

8.4 Preparation

Under USP 795 pharmaceutical compounding, BMC Investigational Pharmacy Service (IPS) will be responsible in maintaining compliance to good compounding practice in preparation of encapsulating dapagliflozin prior to dispensing.

Dapagliflozin (10mg tablets) will be over-encapsulated with **microcellulose**, which will serve as a filler to maintain the study blind. Matching placebo will also be packaged using **microcellulose**. Capsule size required will be determined by IPS with the goal of a minimum capsule size needed for over-encapsulation.

8.5 Medication distribution

Dapagliflozin will be stored in IPS at room temperature (15°C to 30°C [59°F to 86°F]) in a secured area until the time that medication is needed for study subjects. Stability and expiration dates will be monitored by IPS according to the labelling of the medication from the manufacturer and beyond use date in compounding.

IPS will be responsible for manual re-supply to ensure appropriate inventory of dapagliflozin are available upon enrollment and visits.

- How the study medications will be acquired: dapagliflozin will be purchased using funding from American Heart Association for the study.
- Medication distribution, storage and stability: The medication according to labeling as above.
- Dosage, preparation, and administration: subjects randomized to dapagliflozin will receive 10 mg/day during the treatment period.
- Instructions for modification of dose due to toxicity or other reason: If the participant shows any toxicity related to dapagliflozin he/she will be immediately withdrawn from the study.
- Accountability procedures and compliance assessment: Participant will be asked to keep a log of taking medication and to bring their package to each visit for pill count. The investigator will perform a pill count to assess subject compliance. Participants will be withdrawn from the study if their compliance is equal or lower than 80%.

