Randomization: The study statistician at BEDAC will supervise computer generation of the randomization scheme. Randomization scheme will be provided to the IPS team in a blinded manner. Investigators and other team members will not have access to the randomization table. Un-Blinding will occur when all subjects have completed treatment and evaluation of the primary outcome data measures is complete. Un-blinding must be requested by the PI.

Treatment Period: Subjects will be randomized (1:1) to receive dapagliflozin and then placebo or vice versa. Total treatment period when participants are taking medication (either placebo or dapagliflozin) is 12 weeks consisting of 6 weeks of treatment for each dapagliflozin and placebo with 2 weeks of washout period in between. Subjects randomized to dapagliflozin will receive 10 mg/day (in capsule form). Subjects randomized to placebo will receive matching placebo capsule. Treatment order will be block randomized in block sizes of 2 or 4. We will call patients to ascertain compliance at week 3 into each treatment.

Treatment Plan:

The Boston Medical Center Investigational Drug Service will dispense 6 weeks supply of either dapagliflozin or placebo depending on their randomized group. Subjects will be instructed to contact the investigators if they experience adverse events or a change in healthy status.

Study Telephone Call 1: Subjects will be contacted in the 3rd week of the treatment period to evaluate self-reported compliance, assess for any relevant side effects, adverse events and change in clinical status.

Study Visit 2:

After arrival in the research unit, the investigators will perform a pill count to assess subject compliance, and complete an assessment of side effects and any change in clinical status. We will then perform all the study procedures to evaluate vascular health as described from Study Visit 1.

Study Visit 3:

After a washout period of 2 weeks (participants instructed not to take research medications during this time), patients will return to start treatment with either dapagliflozin or placebo for 6 weeks. We will perform all the study procedures from Study Visit 1. When assigned to dapagliflozin, participants will receive 10 mg/day (in capsule form) for the period of treatment. Subjects assigned to placebo will receive matching placebo capsules.

Telephone Call 2: We will call patients at week 3 as described for telephone Call 1.

Study Visit 4:

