After arrival in the research unit, the investigators will perform a pill count to assess subject compliance, and complete an assessment of side effects and any change in clinical status. We will then perform all the study procedures to evaluate vascular health as described from Study Visit 1.

Earlier termination of the study:

There are no procedures in case of earlier termination of the study. All participants can voluntary withdraw from the study without suffering any penalty.

Participants will be withdrawn from the study if their compliance is equal or lower than 80% after performing a pill count on each visit, or if they develop an intervention illness that would impact the interpretation of the study.

10 Assessment of Safety and Data Safety Monitoring Plan (DSMP)

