12.3 Statistical Methods

We will compare baseline and follow-up results for each treatment group using analysis of repeated measures with Proc Mixed in SAS. The measures of endothelial phenotype (EC insulin-signaling) and vascular function (flow-mediated dilation) will be our dependent variables and treatment, period, and sequence will be the main independent measures. That is the variables are denoted as y_{ijk} is the observation for the i^{th} sequence ($i=1,2$) j^{th} subject ($j=1,2,\dots,n$) k^{th} period ($k=1,2$).

The model can be described by:

$$y_{ijkl} = \beta_0 + \beta_1 X_{treat} + \beta_2 X_{period} + \beta_{12} X_{treat} X_{period} + s_{ij} + \varepsilon_{ijk}$$

s_{ij} is a random subject effect term and is assumed to be independently and identically distributed with $N(0, \sigma_s^2)$

ε_{ijk} is an error term and is assumed to be independently and identically distributed with $N(0, \sigma^2)$

Two dummy variables are introduced as:

$X_{treat} = 1$ if the subject is in treatment B, and $X_{treat} = 0$ otherwise;

$X_{period} = 1$ if the subject is in period 2, and $X_{period} = 0$ otherwise;

Model fitting and inference will follow conventional REML analysis in the Proc Mixed procedure in SAS. The between-subject variation includes a carry-over treatment effect and between-subject residuals. The within-subject variation includes direct treatment effect, period effect, and within-subject residuals. A significant period effect reflects evidence of carry-over effect. A significant within-subject treatment effect is consistent with differences between the two treatments adjusting for carry-over and period effect. In exploratory analyses, we will evaluate for effect modification by sex and race. We will evaluate additional exploratory outcomes in a similar fashion.

Analysis Datasets: The intention-to-treat (ITT) analysis dataset will be the source of data for primary analyses. This will include all randomized participants regardless of actual receipt or compliance with therapy. The per protocol analysis will be conducted based on adherence to assigned treatment (defined as more than 80% based on pill returns). Use of Proc Mixed analyses allows all participants to be included if they contribute any data to the analysis dataset.

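### Low pill counts and drug-related toxicity end study participation, not only study drug, so later outcomes that the primary ITT analysis calls for are apparently not collected

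*Combined protocol and SAP*

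**What the plan says.** Section 8.5 has two rules that remove a person from the study. For toxicity: "If the participant shows any toxicity related to dapagliflozin he/she will be immediately withdrawn from the study". For adherence, it sets a cut at 80%, which Section 9 (under the heading on earlier termination) repeats: "Participants will be withdrawn from the study if their compliance is equal or lower than 80% after performing a pill count on each visit". The same part of Section 9 states: "There are no procedures in case of earlier termination of the study". The Schedule of Events has no early-termination visit and no off-drug visit.

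Section 12.3 makes the ITT dataset primary: "This will include all randomized participants regardless of actual receipt or compliance with therapy". It defines the supporting analysis by adherence: "The per protocol analysis will be conducted based on adherence to assigned treatment (defined as more than 80% based on pill returns". Its only provision for incomplete data is: "Use of Proc Mixed analyses allows all participants to be included if they contribute any data to the analysis dataset".

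On sequence, Section 9 says that at Visit 2 "the investigators will perform a pill count to assess subject compliance, and complete an assessment of side effects and any change in clinical status", and the vascular and endothelial cell (EC) procedures come after that. Visit 4 is worded the same way. Section 4.2.1 needs ECs before and after each treatment period, which means all four visits.

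**The concern.** An ITT set defined regardless of compliance needs outcomes from people who comply poorly or stop drug. The conduct rules end participation for those same reasons and do not separate stopping drug from leaving the study. The ITT set keeps such people by name, but their follow-up ends at the trigger.

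Two things are at stake. First, withdrawal applies at 80% or less and per-protocol inclusion at more than 80%. As far as adherence goes, the two analyses can then differ only through visits made up to withdrawal, so comparing them says little about the effect of non-adherence. Second, Section 5.1 justifies the cross-over by comparison within individuals. A person who leaves before Visit 4 gives no complete comparison of that kind. The mixed model uses the visits that exist but cannot supply the others. It then relies on missing at random, for losses set off by side effects or non-adherence.

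**Working it through.** **Visits lost under each rule.** Outcomes are scheduled at Visits 1 to 4 (weeks 0, 6, 8 and 14). Pill counts fall at Visits 2 and 4. Symptoms are assessed at every visit and at the calls in weeks 3 and 11.

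| Trigger | Visits lost | Of 4 |
|---|---|---|
| Toxicity reported before Visit 2 | 2, 3, 4 | 3 |
| Toxicity first disclosed at Visit 2 | 3, 4, and perhaps 2 | 2 or 3 |
| Compliance 80% or less at Visit 2 | 3, 4 | 2 |
| Toxicity in washout or first disclosed at Visit 3 | 4, and perhaps 3 | 1 or 2 |
| Toxicity between Visits 3 and 4 | 4 | 1 |
| Toxicity first disclosed at Visit 4 | none, or 4 | 0 or 1 |
| Compliance 80% or less at Visit 4 | none | 0 |

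The compliance rows assume that the visit goes ahead as sequenced, with procedures after the pill count. The either/or rows arise because toxicity withdrawal is to be immediate while symptoms are assessed before the procedures.

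**Where the compliance cut falls.** Assume 6 × 7 = 42 scheduled doses as the denominator. Then 0.80 × 42 = 33.6. A count of 33 doses (33/42 = 78.6%) triggers withdrawal and 34 (34/42 = 81.0%) does not. Nine missed doses in six weeks are enough.

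**How many people this could involve.** No withdrawal rate by cause is given. Section 12.2 plans 42 randomised and 35 completing: 42 − 35 = 7, or 16.7%, consistent with its 83% (0.83 × 42 = 34.9). It also prints 7% not completing, which is 0.07 × 42 = 2.9, about 3. The two figures conflict, and both cover all causes.

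**What retention would cost the ITT contrast.** This needs an effect in points. The plan's 35 completers do not follow from an effect size of 0.25 read against the SD of differences: a paired t-test at two-sided alpha 0.025 with n = 35 then has about 21% power. I therefore back-calculated the effect that gives 90% power at n = 35. It is 0.619 SD, and 0.619 × 5.8 = 3.59 points on the EC outcome. This is an assumption, not the plan's figure.

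Add k retained participants with zero effect. The contrast is multiplied by p = 35/(35 + k). Power is the upper-tail probability of a noncentral t with n = 35 + k, either with SD 5.8 or with SD widened for the mixture to √(5.8² + p(1 − p) × 3.59²).

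| k | p | Contrast (points) | Power, SD 5.8 | Power, SD widened |
|---|---|---|---|---|
| 1 | 0.972 | 3.49 | 89% | 89% |
| 2 | 0.946 | 3.39 | 88% | 88% |
| 7 | 0.833 | 2.99 | 84% | 82% |

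Zero effect is pessimistic for a low complier, who may have taken up to 33 of 42 doses in one period and goes on to the other treatment.

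**The case against.** The strongest reply is that this is a mechanistic study. It asks what dapagliflozin does to endothelial cells while it is taken, and each extra visit means a catheter in each arm and eight J-wires, possibly in someone who has just reacted to the drug. Ending participation can then be reasonable. Section 12.3 also uses whatever data exist. A low complier at Visit 2 keeps a full period 1 change, and one found at Visit 4 loses nothing.

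Much of this stands for toxicity. A reader might infer that full follow-up of everyone who stops drug would restore the lost within-person comparison. It would not. After toxicity in period 1 with no period 2 capsules, the later visits compare no drug with no drug. They support a treatment-policy estimate and nothing more.

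The reply does not rescue the compliance rule. That rule has no safety basis, the affected person could still take period 2 medication, the per-protocol analysis already serves the on-drug question, and the plan itself chose ITT as primary.

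It can also be said that no sentence forbids collecting outcomes after withdrawal, and that the statement about absent procedures could refer to the trial itself stopping early. That is fair, although the sentences around it concern participants. Section 10.2 leaves withdrawal after a serious adverse event to the principal investigator, but it adds no outcome follow-up.

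**Conclusion.** The concern holds in a limited form. Read as written, the withdrawal rules drop outcomes that the primary ITT analysis calls for, and the analysis plan has no means of recovering them. The compliance rule costs data only when it is triggered at Visit 2 (2 of 4 assessments). The toxicity rule costs up to 3 of 4.

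Three stronger readings are not supported:

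- **A known bias in the treatment effect.** The documents give no withdrawal rate by cause and no link between withdrawal and EC response, so neither size nor direction can be derived. The adverse-effect rates in Section 6.1 are not withdrawal rates, and toxicity is not defined.
- **A ceiling of 7 of 42 on the losses.** That is a planning estimate, it conflicts with the printed 7% (about 3 of 42), and nothing caps the losses.
- **Removal of withdrawn people from the ITT set.** They stay in it with the visits already made.

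The number affected is probably small. The conclusion rests on reading withdrawal from the study, with no post-withdrawal visit described, as the end of outcome collection. The change is recommended because it is cheap and because uncollected outcomes cannot be recovered later.

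**What to change.** 1. **Sections 8.5 and 9, compliance.** Delete study withdrawal for compliance of 80% or less. These participants go on to washout, period 2 and all visits, stay in the ITT set, and are excluded only from the per-protocol analysis.
2. **Section 8.5, toxicity.** Stop study drug immediately. Where it is clinically safe and the participant agrees, do the end-of-period assessment for that period before participation ends, including EC collection if accepted. Record whether the participant was on or off drug at that assessment.
3. **Optional.** Further off-drug visits may be added if the sponsor wants a treatment-policy ITT estimate, with their limited purpose stated.

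The cost is some wording and a few visits, nearly all already scheduled. Each is a fasting visit of about two hours with invasive cell collection, and some participants will decline all or part of it. The ITT contrast is slightly diluted: about 3% to 5% for 1 or 2 retained participants with zero effect, with power about 88% to 89%. If as many as 7 were retained with zero effect, it would shrink by 17% and power would be about 82% to 84%. All these figures use the assumed 3.59-point effect.

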8.6 Emergency Unblinding

There may be circumstances where it is necessary to unblind the subject's treatment assignment due to clinical care or ingestion of study medication by household member (ie child). The treating clinician will contact with study principal investigator to request emergency unblinding and provide the reason for unblinding. The emergency unblinding request will be sent to the IPS service by telephone during business hours and by email to [contact] as well as paging the investigational pharmacist on call ([name]) and the investigational pharmacist will provide the treatment assignment to the clinician.

9 Study Procedures

Recruitment

We will use two methods for recruiting participants in this study: 1) Recruitment within the internal medicine, endocrinology and cardiovascular clinics by study investigators who are also the care providers for potential participants as well as by care providers who are not also investigators on this study; 2) Recruitment using advertisements in the form of flyers in the endocrinology and cardiovascular clinics or on social media.

1. Recruitment in outpatient clinical practices

The study coordinator will check the EMR and clinic schedule for subjects who meet inclusion/exclusion criteria (if subjects do not have a recent HbA1C result or pregnancy status is not clear, subjects will still be considered as these assays can be done as part of a screening visit following full consent). The study coordinator will alert providers that a potential subject is to be seen in the clinic. If the provider agrees that the subject may suitable for the study, they will inform the subject about the study and if there is interest, they will notify the study coordinator.

The study coordinator will contact the potential subject and tell them more about the study. If they continue to be interested, the coordinator will move onto the telephone screening process. If they are not interested then only their name/EMR# and “not interested” will be kept in a separate log to prevent them from being contacted a second time.

2. Advertising in Clinics and Social Media

Advertisements will be posted within endocrinology and cardiovascular and internal medicine and family medicine clinics and flyers available for patients to view and on social media. If interested based on their review of the information on the flyer they can call the study team via the phone number on the flyer. These materials will be approved by BU Communications before being posted.

For those individuals who call in after seeing a flyer or advertisement about the study, the study coordinator will contact the individual and briefly review pertinent details about the study. If they continue to be interested, the coordinator will move onto the telephone screening process. If they are not interested then only their name/EMR# and “not interested” will be kept in a separate log to prevent them from being contacted a second time.

See “Recruitment Script” and other recruitment materials

Screening (prior to full consent)

EMR screening will be done by the study coordinator to determine initial eligibility. If subjects are interested in the study following the recruitment phone call, the coordinator will read them the full screening consent with HIPAA language. The procedures that will then be done are additional EMR review and screening questions. The EMR has to be accessed to establish whether or not the subject will need a screening visit for bloodwork or whether they can start the study without a screening visit. After this has been done, the coordinator will contact the subject to tell them whether they are eligible

For those subjects who do not continue to full consent, the only information that will be kept will be names/EMR and whether the potential subject was eligible or not, and interested or not. The primary reason this information will be kept will be to avoid recontacting individuals who decline or who are not eligible so as not to disrupt clinic flow unnecessarily. For subjects who go on to participate in the study, the screening data will become part of their study record.

For all subjects who agree to be screened, we will use the full screening consent with HIPAA language. We will request a partial HIPAA waiver to request that the signature be waived. Given the fact that we will be screening by phone as it is not possible to screen in person at the clinic due to clinic flow, and the fact that our BMC population by and large do not have the technological capacity to sign authorization in REDCap, we feel that not obtaining a signature is reasonable. If we do have to obtain a signature using REDCap, we may not be able to enroll many of our BMC patients.

Screening Visit (up to week -4) (30 minutes):

There are two possible pathways for obtaining the screening information that includes both medical history and laboratory values (HgA1c and pregnancy test for people of child-bearing potential). If participants have an available HgA1c within the past 3 months and are not of child-bearing potential, we will offer the subject the option of completing the screening visit on the same day as Study Visit 1. In this case, the subject will be instructed to come to the laboratory fasting and if applicable to avoid smoking on the morning of the study.

All other potential subjects will have a screening visit that is separate from study visit 1 and will not have to modify eating or smoking on the day of the screening visit.

For all potential subjects: After obtaining informed consent from the subject, investigators will review again the subject's medical history to confirm eligibility. Patients will undergo HbA1c testing unless they already have testing done in the last 3 months. For people of child-bearing potential, a blood based pregnancy test will be sent to the clinical laboratory at BMC.

After eligibility is confirmed, the first study visit will be scheduled either at a future date or on the same day as the screening visit.

For all 4 study visit: subjects will be instructed to fast after midnight on the day of the study, and if applicable, to avoid smoking on the morning of the study. Each study visit lasts about 2 hours.

Study Visit 1: patients will arrive at vascular research unit at Boston University School of Medicine ([name]) in the morning. Vital signs will be measured and blood will be collected. We will then assess vascular function as follows:

1. **Endothelial vasodilator function (30minutes):** Brachial artery endothelium-dependent flow-mediated dilation and extent of reactive hyperemia will be measured using vascular ultrasound and fingertip tonometry as previously described ²⁰. Briefly, we will record 2-dimensional images and Doppler signals from the brachial artery and pulse signals from the fingertip at baseline and after 5-minute cuff occlusion of the upper arm and small arteries in the finger. After 10 min of

cuff release we will re-acquire the same image of the brachial artery scan before nitroglycerin administration. The patient will be given 0.4 mg of sublingual nitroglycerin, and 2 minutes 15 seconds after its administration images of the brachial artery will be acquired for 60 seconds.

2. **Arterial stiffness measurement (15 minutes):** Compliance of the central aorta and upper extremity will be assessed by measuring carotid-femoral and carotid-radial pulse wave velocity (PWV). A small probe is used to record signals from the carotid, radial, and femoral arteries.
3. **Endothelial cell collection (one hour):** We will place a 20-gauge intravenous catheter in an arm vein in each arm. Endothelial cells will be collected utilizing a J-wire inserted into the intravenous catheter ^{21, 22}. The J-wire is passed into the intravenous catheter and gently makes contact with the endothelial surface to collect cells which are then washed from the wire into physiological buffer. The typical yield is 200-400 cells per wire. Depending on the availability and quality of the arm veins, the investigator may use local anesthesia with 0.5 to 1.0 ml of 1% lidocaine injected subcutaneously. We will collect cells using four wires on each arm for total of eight wires.
4. **Biochemical analysis of plasma and serum:** The blood samples will be processed in the Clinical Chemistry Laboratory at Boston Medical Center to measure fasting glucose, insulin, and lipids. Serum, plasma, and white blood cell samples will also be collected and stored at -80° C for additional analyses of biomarkers relevant to cardiovascular health and for miRNA analysis.
5. **Biorepository:** Serum, plasma, and white blood cell samples will also be saved for future analyses. These samples will be stored in a -80° C freezer in the principal investigator's laboratory ([name]) with key card only access.

Randomization: The study statistician at BEDAC will supervise computer generation of the randomization scheme. Randomization scheme will be provided to the IPS team in a blinded manner. Investigators and other team members will not have access to the randomization table. Un-Blinding will occur when all subjects have completed treatment and evaluation of the primary outcome data measures is complete. Un-blinding must be requested by the PI.

Treatment Period: Subjects will be randomized (1:1) to receive dapagliflozin and then placebo or vice versa. Total treatment period when participants are taking medication (either placebo or dapagliflozin) is 12 weeks consisting of 6 weeks of treatment for each dapagliflozin and placebo with 2 weeks of washout period in between. Subjects randomized to dapagliflozin will receive 10 mg/day (in capsule form). Subjects randomized to placebo will receive matching placebo capsule. Treatment order will be block randomized in block sizes of 2 or 4. We will call patients to ascertain compliance at week 3 into each treatment.

Treatment Plan:

The Boston Medical Center Investigational Drug Service will dispense 6 weeks supply of either dapagliflozin or placebo depending on their randomized group. Subjects will be instructed to contact the investigators if they experience adverse events or a change in healthy status.

Study Telephone Call 1: Subjects will be contacted in the 3rd week of the treatment period to evaluate self-reported compliance, assess for any relevant side effects, adverse events and change in clinical status.

Study Visit 2:

After arrival in the research unit, the investigators will perform a pill count to assess subject compliance, and complete an assessment of side effects and any change in clinical status. We will then perform all the study procedures to evaluate vascular health as described from Study Visit 1.

Study Visit 3:

After a washout period of 2 weeks (participants instructed not to take research medications during this time), patients will return to start treatment with either dapagliflozin or placebo for 6 weeks. We will perform all the study procedures from Study Visit 1. When assigned to dapagliflozin, participants will receive 10 mg/day (in capsule form) for the period of treatment. Subjects assigned to placebo will receive matching placebo capsules.

Telephone Call 2: We will call patients at week 3 as described for telephone Call 1.

Study Visit 4:

After arrival in the research unit, the investigators will perform a pill count to assess subject compliance, and complete an assessment of side effects and any change in clinical status. We will then perform all the study procedures to evaluate vascular health as described from Study Visit 1.

Earlier termination of the study:

There are no procedures in case of earlier termination of the study. All participants can voluntary withdraw from the study without suffering any penalty.

Participants will be withdrawn from the study if their compliance is equal or lower than 80% after performing a pill count on each visit, or if they develop an intervention illness that would impact the interpretation of the study.

10 Assessment of Safety and Data Safety Monitoring Plan (DSMP)

